5.5.2 Treatment Allocation

Participants randomised to start drug will be provided with their allocated drug/s after randomisation at the baseline visit, which they will start on the next day (i.e., day 1, week 1). In the event that there is any delay between receiving the trial tablets and starting the treatment, then the patient will receive a reminder telephone call shortly before the day that the medication should be commenced. The first day of treatment defines day 1, week 1. Delay between randomisation and receipt of IMP will not be a deviation but will be recorded in the CRF.

Participants will be supplied with trial tablets from the hospital pharmacy to cover a maximum period of six months. Detailed dated instructions on dosing will be provided in the patient pack. The participant will be telephoned between the end of weeks 1 and 2 and between the end of weeks 3 and 4 by the site staff, and other times during drug introduction as necessary, as well as routine follow-up time points, to ensure they are taking the medication correctly.

Drugs will be provided in their packs as marketed and licensed (i.e. unaltered) and dispensed by the participating hospital pharmacy under research protocols.

5.5.3 Emergency Unblinding Procedures

If the patient develops a contraindication to the trial medications, the medication should be stopped in line with SPC guidance. Similarly, if the patient develops a definite indication for the trial medications the study medications should be stopped as per the SPC.

As this is an open label trial, it should not be necessary to unblind the allocated treatment. If identification of the trial drug is considered necessary, the tablets can simply be examined and identified as cilostazol or ISMN as they will be dispensed in their licensed packaging.

5.6 WITHDRAWAL OF STUDY PARTICIPANTS

Participants are free to withdraw from the study at any point or a participant can be withdrawn by the Investigator. If withdrawal occurs, the primary reason for withdrawal will be documented in the participant's case record form if possible. The participant will have the option of withdrawal from:

- (i) study medication with continued study procedures and collection of clinical and safety data;
- (ii) study medication and follow-up visits (or study procedures) with continued collection of clinical and safety data from medical notes
- (iii) Consent to be contacted about other research studies
- (iv) all aspects of the trial but continued use of data collected up to that point. To safeguard rights, the minimum personally identifiable information possible will be retained.

Randomised patients who wish to be withdrawn from the study before they have undertaken any study related procedures will be withdrawn from the study and

another participant will be recruited to replace them. Data on the original participant will be kept on the CRF/database if the participant agrees to this.

Trial medication may be stopped at any time by the Investigator or treating physician if deemed advisable. Stopping trial medication on its own does not necessarily equate with withdrawal from the trial, and follow-up procedures will continue unless the participant withdraws consent. Participants who wish to withdraw from follow-up will not be able to continue on the IMP. Participants may wish to withdraw from active participation in follow-up by central co-ordinators but agree that relevant information can be obtained from their hospital or GP records. Participants may withdraw consent to be contacted about other research but this will not affect their continued participation in LACI-3. These scenarios will be documented and kept up to date in the CRF.

If after randomisation into LACI-3, a participant subsequently is found to have a condition which would have made them ineligible for recruitment, these participants will be retained in the trial, at least for the purposes of follow-up, to protect the 'intention to treat' principle of analysis, and a decision for the continuation of the IMP will be made by the Principal Investigator or designee with the participant (or their relatives in the event of loss of capacity) on the basis of safety.

A recurrent event, such as stroke or other outcome, or SAE s not of itself a reason for withdrawal or discontinuation of IMP. In legal terms, consent to participate is assumed to remain valid if mental capacity is lost during the trial. Hence, the participant who loses capacity will remain in the trial unless their doctor or representative considers it necessary to withdraw some or all aspects of their participation. In making such decisions, the doctor or representative will consider the participant's wishes and feelings before the loss of capacity.

Delegated research team members will follow the appropriate local regulations (Mental Capacity Act 2005 for England and Wales and Adults with Incapacity (Scotland) Act 2000 for Scotland) and guidance regarding loss of mental capacity in research to determine if the consent remains valid after loss of capacity. If it is agreed that the participant should be withdrawn from the study medication, follow-up or all aspects of the trial, a delegated research team member will record it on e-CRF.

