The LACunar Intervention Trial 2 (LACI-2) trial was funded mainly by the British Heart Foundation (BHF) and was conducted in 26 centres in the UK between Feb 2018 and end of May 2021, (registration EudraCT 2016-002277-35, ISRCTN 14911850, MHRA 01384/0252/001-0004), aiming to recruit 400 patients.⁴⁷ LACI-2 was open label with blinded centrally-collected outcomes (PROBE) design since no placebo was available and overencapsulation was not possible. LACI-2 used the same partial factorial design as LACI-1 (ISMN vs cilostazol vs ISMN+cilostazol vs neither, in a partial factorial design, with all patients receiving guideline-based secondary stroke prevention) but the drugs were administered for 1 year. Drug was supplied by hospital pharmacies, via the AcoRD process, hence several generic brands could be used in LACI-2, as long as at the correct dose. LACI-2 aimed to determine feasibility, tolerability, safety and recorded outcome event rates to determine event rates to power a larger trial and identify any efficacy signals to help justify a large phase 3 trial.⁴⁷ LACI-2 used a composite outcome of any recurrent stroke or TIA, MI, dependency (mRS>2), any cognitive impairment or death. LACI-2 also used an ordinal score of cognitive status based on DSM-5 definitions, using data from the tMoCA, TICS, animal naming, and any clinical dementia diagnosis, developed in a large UK study of cognitive impairment after stroke.⁴⁸ All analyses were adjusted for minimisation variables (baseline age, sex, NIHSS, mRS, sBP, smoking status, time after stroke, and years of education) and cognition was also adjusted for baseline MoCA.

LACI-2 recruited 363 of the planned 400, stopping at 363 since this was deemed enough to demonstrate feasibility, tolerability and safety and had been disrupted by COVID-19. The one-year follow-up ended in May 2022.⁴⁹ Recruitment stopped completely due to the Covid-19 pandemic for four months and delayed recruitment thereafter.

LACI-2 met its primary feasibility targets, recruiting 363/400 target patients (impact of COVID-19), median age 64 [interquartile range 56.0-72.0] years, 251/363 males (69.1%), at median 79 days after stroke, and baseline characteristics were well-balanced.

LACI-2 retained 358 (98.6%) at 12 months, and exceeded the tolerability target of 75% taking \geq 50% of allocated drug, and indicating good drug tolerance.

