There were no safety concerns, with only four deaths and four haemorrhages (all were systemic), and few SAEs of which only two were possibly related to either drug. LACI-2 also provided efficacy signals. It showed that, in comparison with no drugs: neither ISMN nor cilostazol alone reduced the composite outcome (n=297; ISMN adjusted hazard ratio, aHR, 0.80, 95%CI 0.59-1.09, p=0.16; cilostazol aHR 0.77, 0.57-1.05, p=0.10). Individually, ISMN reduced recurrent stroke (adjusted odds ratio aOR 0.23, 0.07-0.74, p=0.014), and cognitive impairment (aOR 0.55, 0.36-0.86, p=0.008); cilostazol reduced dependency (aHR 0.31, 0.14-0.72, p=0.006); ISMN+cilostazol reduced the composite (aHR 0.58, 0.36-0.92, p=0.02), dependency (aOR 0.14, 0.03-0.59, p=0.008), any cognitive

impairment (aOR 0.44, 0.23-0.85, p=0.02), and improved QoL (aMD 0.10, 0.03-0.17, p=0.005).^{49,50}

These findings were supported by the results of the patient-reported Stroke Impact Scale (global and individual domains) and an analysis of Global Clinical Outcome (recurrent ordinal stroke, ordinal MI, ordinal 7-level cognition, ordinal mRS, quality of life [full Health Status Utility Score of the EQ-5D], the Zung depression score full scale, and the binary status of alive or dead).

LACI-2 showed that the trial design was feasible, ISMN and cilostazol were well-tolerated and safe individually and in combination. They may reduce recurrent stroke, dependency, and cognitive impairment after lacunar stroke, improve QoL, and could prevent other adverse outcomes in SVD, and should be tested in large phase 3 trials.

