9.2 PROPOSED ANALYSES

All analyses and presentation of the results will be in accordance with CONSORT guidelines including on factorial trials.⁶⁶ All analyses will be intention to treat. A full statistical analysis plan will be developed and published prior to database lock including use of imputation or complete case analysis and sensitivity analyses. Numbers (%), median [interquartile range] or mean (SD) will be used as appropriate to summarise data, with 95% confidence intervals (CI). Main outcomes will be presented for the whole population and by sex. Participants who die will be included in the DSM-5 7 level ordinal cognitive and mRS scores, and for scores without a category for death will have a score worse than any living score assigned to maintain power and prevent missing any 'kill or cure' effect. Multiple testing adjustments will be used where relevant.

Analyses will use, as appropriate: binary logistic regression (BLR, presented as adjusted odds ratio, aOR), Cox proportional hazards regression (CPHR, adjusted hazard ratio, aHR), ordinal logistic regression (OLR, presented as aOR), or multiple linear regression (MLR, presented as adjusted mean difference, aMD). 95% confidence intervals (CI) will also be given.

Analyses will be adjusted for stratification (MoCA) and minimization variables (baseline age, sex, NIHSS, mRS, SBP, smoking status, time after stroke, years of education). Additional adjustments will be used where relevant and feasible, e.g. treatment duration, visible infarct y/n and SVD burden.

The Primary outcome is an ordinal adjusted analysis of the DSM-5 7-level cognitive score at 18 months.

Secondary outcomes will be analysed including all available data, using:

-*MLR*: 7-level ordinal mRS, 4-level DSM-5 cognitive score, cognitive tests individually (MoCA, TICS); Quality of Life (EQ-5D, Health Status Utility Value and VAS); mood (Zung); Stroke Impact Scale individual domains and overall score;

-BLR: dependency [mRS>2] vs no dependency; death; recurrent ischaemic or haemorrhagic stroke or TIA, or MI, individually; systemic haemorrhage; symptoms; SAEs, SARs, SUSARS – events that meet these definitions as per protocol and that are not already reported as formal outcomes;

-CPHR: death; and a Composite Outcome (recurrent stroke or TIA, MI, dependency [mRS>2], any cognitive impairment, death) using patients with complete data for all required variables, adjusted for baseline variables;

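### The main Cox analysis of the secondary composite is limited to complete-data participants, which can leave out people who have already met it; the replacement sentence in section 5.6 needs only a clarification

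*Protocol*

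**What the plan says.** Section 9.2 sets the general rule: "All analyses will be intention to treat". It introduces the secondary outcomes by saying that they are analysed with the data available. For the Composite Outcome (recurrent stroke or TIA, MI, dependency, any cognitive impairment, death) it specifies Cox regression "using patients with complete data for all required variables, adjusted for baseline variables". Under the sensitivity analyses, the same section repeats the composite in everyone who has any of the data needed. The Global Clinical Outcome, also in section 9.2, uses all patients. For the primary outcome, the choice between imputation and complete cases is left to the statistical analysis plan.

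Section 5.6 covers "Randomised patients who wish to be withdrawn from the study before they have undertaken any study related procedures". They are withdrawn, and "another participant will be recruited to replace them". It adds: "Data on the original participant will be kept on the CRF/database if the participant agrees to this". It does not say whether they stay in the analysis set. The same section keeps participants found ineligible after randomisation, for the sake of intention to treat. Section 5.4 puts only people who consented but were never randomised outside the intention-to-treat population.

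**The concern.** Whether a participant has complete data is known only after randomisation. Limiting the main analysis of a time-to-event composite to such people conflicts with the two general statements in section 9.2. It also discards information that has already been collected: one observed component is enough to meet the composite, so a missing value on another component cannot undo it. Cox regression handles partial follow-up by censoring, so the method does not require the restriction.

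At stake are observed events and precision on one secondary outcome. There is also a possible selection effect if people who cannot complete telephone testing are sicker and if such losses differ by arm.

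The replacement sentence raises a smaller question. The trial is open label, so a participant who leaves soon after randomisation may know the allocation. A site or analyst could read the word replace as meaning that the leaver no longer counts.

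**Working it through.** **Composite: how the components are collected (section 6.9).**

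- Stroke, TIA, haemorrhage and MI come from questionnaires and also from checking medical notes.
- The modified Rankin score can come from local staff or from a relative or carer if the participant cannot be reached.
- Cognition needs the tMoCA, TICS and animal naming, done by telephone by the central team.
- Death is a level of the cognitive scale (section 9.2), so a participant who dies is not missing on cognition.

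An event can therefore be on record while the cognitive component is missing. Under the main rule that participant is left out; under the listed sensitivity analysis the same participant is kept. The affected group is mainly living participants with a recorded stroke, TIA, MI or dependency and no cognitive assessment.

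**Sample size in section 9.1, reproduced first.** Inputs: control distribution 0.35, 0.24, 0.12, 0.20, 0.03, 0.03, 0.03; common odds ratio 0.70; alpha 5% (two-sided assumed, since sidedness is not stated); power 90%; losses 15%. Whitehead's proportional-odds formula, with p̄ the mean of the two arms' distributions:

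N = 12(1.960 + 1.282)² / [ (ln 0.70)² × (1 − Σp̄³) ] = 1079 evaluable

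1079 / (1 − 0.15) ≈ 1270 randomised, which agrees with the stated 1300 after rounding up.

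**Number the composite rule could leave out.** Section 9.2 says the inflation covers up to 15% missing primary (cognitive) outcome data.

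- 0.15 × 1300 = 195 left out
- 1300 − 195 = 1105 kept

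The figure of 195 counts everyone without a cognitive outcome, not only those with an observed event. Gaps in other components or in covariates could add to it.

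**Replacement: passages side by side.** Section 5.5.1 stratifies randomisation by baseline MoCA and minimises on other baseline variables. Section 6.9 collects these after consent and before randomisation. Nobody can then be randomised without having undergone baseline procedures, so the trigger in section 5.6 can hardly apply as written. Replacement is not needed for power either: by the same formula, 1105 evaluable participants give 90.7% power at an odds ratio of 0.70, with early leavers counted within the 15%.

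**The case against.** **On the composite.** The wording refers to required variables and does not say every component, so leaving out a participant with a known stroke is an inference. The inclusive analysis is already prespecified, the outcome is secondary, and section 9.1 reports no differential loss between groups in LACI-2. Censoring people without a cognitive test has its own weakness: it assumes that censoring is unrelated to prognosis, which is doubtful if missing tests go with poor cognition.

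Most of this stands as a limit on the size of the point. It does not remove the conflict. A sensitivity analysis that admits people with missing data shows that the main analysis excludes them, and the restriction still disagrees with the general statements in the same section. The protocol does not show that bias would result.

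A reader might take LACI-2 as evidence of how much the rule costs, because "LACI-2 retained 358 (98.6%) at 12 months" of 363 randomised while its composite result is given for n=297. The protocol does not say why those numbers differ, so they cannot be attributed to a complete-data rule or projected to LACI-3.

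**On replacement.** A reader might infer that section 5.6 drops randomised people from the analysis and so biases the primary comparison. The text does not say so, and sections 5.4, 5.6 and 9.2 together point to keeping everyone randomised. A leaver's outcome is missing whether or not someone else is recruited, and nothing says the new recruit takes over the leaver's allocation. The protocol gives no early-withdrawal rate, so any odds ratio for such a bias would rest on invented, one-sided numbers. This objection stands in full, and only the unclear wording remains.

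**Conclusion.** The point holds for the composite, at modest weight. The protocol makes the restrictive analysis the main one and the inclusive analysis the secondary check, against its own general rules. It could leave out up to about 195 of 1300 participants, assuming that missing cognitive data reach the planned 15% and that the required variables include the cognitive component. The number of recorded events lost is unknown. The primary outcome carries no such restriction, and the sample size is not in question.

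The replacement sentence is not an error. It needs a clarification because its trigger hardly fits anyone who has been randomised and because it leaves the leaver's analysis status unstated.

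**What to change.** 1. In section 9.2, make the main Cox analysis of the composite include all randomised participants with any follow-up. Count the first observed component as the event and censor the others at their last assessment. Keep the complete-data analysis as the sensitivity analysis.
2. In section 5.6, state that any recruited replacement is additional and that the participant who left stays in the allocated arm of the intention-to-treat set. Reword the trigger so that it can apply to someone who has been randomised.

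Both are wording changes and the sample size stays at 1300. The cost of the first is reliance on non-informative censoring for people without a cognitive test; the retained complete-data analysis helps to probe that. Under the second, early leavers without outcomes count as missing, within the 15% already allowed.

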6. INVESTIGATIONAL MEDICINAL PRODUCT AND PLACEBO

6.1 STUDY DRUG

6.1.1 Study Drug Identification

The IMP is defined by the active substance only, therefore all authorised brands may be used.

Oral cilostazol or ISMN slow release will be prescribed as per the brand available in the participating hospital pharmacy.

Cilostazol, generic, as 50mg or 100mg tablets.

Isosorbide mononitrate slow release, generic, as 25mg XL, 30mg XL,50mg XL or 60mg XL tablets to the suggested target dose of 40-60mg daily

Isosorbide mononitrate, generic, as 20mg or 40mg tablets to the suggested target dose of 40-60mg daily.

Most isosorbide mononitrate preparations are slow release in the UK. However, where slow release preparations of isosorbide mononitrate are not available, then non-slow release

preparations may be used, but the dose should be split half in the morning (e.g. 08.00 am) and half in the evening (e.g. 18.00hrs). Non-slow release preparations may only be available in 20mg tablets in which case the 20mg should be substituted for the 25mg dose. A target dose of ISMN is 40-60mg daily. Detailed prescribing and administration instructions will be provided in the study treatment pack.

Several doses and brands of these drugs are marketed in the UK, examples are given below as listed in the representative SPCs in section 6.1.3.

- Cilostazol
 - Cilostazol 100 mg Tablets (Generics [UK] Ltd t/a Mylan, [name]
- Isosorbide mononitrate
 - Isodur 25XL Capsules (Galen Limited, [name].
 - Isosorbide Mononitrate Tablets 20 mg (Dexcel Pharma Ltd, [name])

Cilostazol and ISMN are both licensed products for treatment of vascular diseases in Europe and the example summaries of the product characteristics are appended to this trial protocol.

6.1.2 Study Drug Manufacturer

No specific drug manufacturer is required for the trial. All drugs are available from several providers in the UK. Pharmacies may provide the brand of each drug that is available to them.

Refer to the separate document of the representative SPC example of the drug manufacturers provided for LACI-3 investigators and section 6.1.1 above

6.1.3 Marketing Authorisation Holder

The representative SPCs for Cilostazol (Cilostazol 100mg Tablets; marketing authorisation number PL 04569/1427) and Isosorbide mononitrate (Isodur® 25 mg XL capsules; marketing authorisation number PL 27827/0021 and (Isosorbide mononitrate (ISMN) 20mg tablets; marketing authorisation number PL PL 14017/0011) are provided in a separate document with a cover sheet and signature page (signed and verified by the CI and Co-Sponsors) and filed in the trial master file (TMF). Please refer to the representative SPCs.

- Cilostazol
 - Cilostazol 100 mg Tablets
 - Marketing authorisation number PL 04569/1427
- Isosorbide mononitrate
 - Isodur 25XL Capsules
 - Marketing authorisation number PL 27827/0021
 - Isosorbide Mononitrate Tablets 20 mg
 - Marketing authorisation number PL PL 14017/0011

6.1.4 Labelling and Packaging

The IMP will be clearly labelled for clinical trial use only with the trial specific label by the issuing pharmacist. The participant's trial ID number will be displayed on the study treatment pack.

Each pack will be labelled in accordance with Annex 13 of Volume 4 of The Rules Governing Medicinal Products in the EU: Good Manufacturing Practices, with the primary and secondary packaging remain together throughout the trial. They will include storage conditions for the drug, but no information about the patient.

Detailed prescribing and administration instructions will be provided with the study treatment pack. Dose initiation in first 2-4 weeks will be guided by a regular phone calls and instructions.

Medication labels will be in the local language and comply with the legal requirements of Annex 13 of the European Union's Good Manufacturing Practice (GMP). They will include storage conditions for the drug, but no information about the patient.

6.1.5 Storage

The trial drugs will be stored in participating hospital pharmacies as per requirements for the branded products. They will be stored in a restricted access area where temperature is monitored according to the storage instruction in the SPCs. Drug will be delivered to hospital pharmacies as per Manufacturer's usual delivery practices

